### 13.3 Primary Analyses

#### 13.3.1 Safety

Safety evaluations will consist of AEs, application site local tolerability, physical examinations, vital signs, ECGs, and laboratory measurements (hematology, chemistry, and urinalysis).

- Adverse events:
  - Adverse events will be mapped to standard terms, i.e., MedDRA System Organ Class and Preferred Term.
  - Adverse events that occurred during the screening period will be listed separately and will not be included in the AE tabulations.
  - Adverse events that start on or after first dose will be considered a TEAE. At each post-baseline visit, the number and proportion of subjects reporting any given TEAE will be tabulated by severity; each subject will be counted only once according to the worst severity reported up to the current visit. Separate tables will be constructed for (a) all reported TEAEs, (b) protocol treatment related TEAEs, (c) serious TEAEs, and (d) TEAEs leading to protocol treatment discontinuation.
- At each applicable visit, local tolerability (burning, itching, stinging, scaling, and erythema at either axilla) will be described by severity as defined in Appendix E. Subject and Investigator assessments will be included in separate tables and listings, with the count and percentage of subjects within each severity (maximum severity assessed at either axilla) presented by parameter and visit.
- Vital signs will be summarized similarly as for laboratory parameters but without shift tables.
- Laboratory parameters will be descriptively summarized (mean, SD, median, minimum, maximum) for values at each visit and for changes from baseline at each subsequent visit. In addition, at each post baseline visit, parameter status (low, normal, high) will also be summarized as shift tables vs. baseline status.
- Descriptive statistics and/or frequency tables will be prepared as appropriate for physical examinations, and ECG (HR, QTcF, PR, and QRS) parameters, and abnormalities (e.g., normal; abnormal, not clinically significant; abnormal, clinically significant).
- Concomitant medications will be mapped according to the World Health Organization Drug Dictionary (WHODD) and will be presented in data listings.

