4.5.1 Criteria for Premature Discontinuation

4.5.1.1 Discontinuation from Treatment

A subject must be permanently discontinued from the study drug for any of the following reasons:

- The subject becomes pregnant.
- Allergic or adverse reaction to the study drug.
- Clinically significant AE, which in the opinion of the Investigator, or SRC, would put the subject at unnecessary risk if dosing was continued.
- The subject's axillary hyperhidrosis worsens and requires alternative or supplemental medication during the study.

If a subject is discontinued from treatment, he or she should continue to be followed in the study per the [SCHEDULE OF ACTIVITIES](#). If subject refuses to stay in the study, then he or she will be encouraged to complete the Early Termination Visit 7 study procedures.

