7.5 Unscheduled Additional Visit(s)

An unscheduled visit may occur between visits to evaluate AEs, as applicable. An additional unscheduled visit will be scheduled every 7 to 14 days in order to follow-up on unresolved AEs or laboratory abnormalities that were still present at the final Visit 8 (Week 26).

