10.5.3 Time Period for Collecting Pregnancy Information

Females of child bearing potential should be instructed to contact the Investigator immediately if they suspect they might be pregnant (e.g., missed or late menstrual period). If a subject or Investigator suspects that a subject may be pregnant at any time during the study, the investigational product must be withheld until the results of laboratory pregnancy testing are available. If pregnancy is confirmed, the subject must not receive or apply further investigational product and must be discontinued from the study.

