## 7.2 Endpoints

### 7.2.1 Primary Endpoints

#### 7.2.1.1 Safety

- Incidence and severity of application site burning, itching, stinging, scaling and erythema
- Incidence and severity of all AEs and their relationship to study drug
- Incidence of clinically meaningful change from baseline in safety laboratory parameters, physical examination, 12-lead ECGs and vital signs
- Proportion of subjects who discontinue treatment due to an AE

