### 12.3 General Considerations for Analysis

#### 12.3.1 Safety and Efficacy Analysis

- The Safety population will be used for evaluation of safety and efficacy parameters.
- Analyses of safety and efficacy data will be performed in Statistical Analysis System (SAS) software version 9.2 or higher (SAS Institute Inc., 2008).
- The final analysis will be conducted after all subjects have completed the study and the database is locked. Listings will report all data collected in the database.
- If a data table is sparse, only a listing will be presented. Unless otherwise stated, all listings will be sorted by subject number and visit date. Continuous variables will generally be summarized using means, medians, standard deviation (SD), minimum, and maximum. Discrete variables will be summarized by frequency and percentages.
- Summary tables will indicate the number of subjects with complete data for each measurement, event, or outcome.
- Data will be summarized in plots organized by time point and over time.
- For multiple or repeated assessments for the same visit, the latest assessment will be included in the summary tables.
- Summary tables will only include data from scheduled visits.
- Data from unscheduled visits will be included in the listings.
- If additional analyses are required to supplement the planned analyses, they may be performed and will be identified in the appropriate section of the clinical study report

(CSR). Any substantial deviations from the planned SAP will be updated in the SAP and approved.

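### Local tolerability is a primary endpoint, but the SAP describes only visit-by-visit severity counts and no table of how many subjects were ever affected or how badly

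*SAP*

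**What the plan says.** SAP 7.2.1.1 names the endpoint: "Incidence and severity of application site burning, itching, stinging, scaling and erythema". Protocol 3.2.1.1 agrees.

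SAP 13.3.1 gives the analysis. Subject and investigator assessments go into separate tables and listings, "with the count and percentage of subjects within each severity (maximum severity assessed at either axilla) presented by parameter and visit". For TEAEs the same section uses a cumulative rule: "each subject will be counted only once according to the worst severity reported up to the current visit". No such rule is given for tolerability.

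SAP Appendix A, headed as preliminary, lists shift tables with incidence and severity in their titles for burning, itching, dryness, scaling and erythema. It does not say whether the value shifted to is each visit's or the subject's worst. Stinging has no table. Dryness has one, although neither tolerability scale (SAP Appendix E) collects it. Listing 16.2.7.7 makes the same substitution.

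SAP 12.3.1 sets two general rules: "Summary tables will only include data from scheduled visits", and "For multiple or repeated assessments for the same visit, the latest assessment will be included in the summary tables". Protocol 7.5 adds: "An unscheduled visit may occur between visits to evaluate AEs, as applicable".

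On follow-up after stopping the gel, Protocol 4.5.1.1 says of such a subject that "he or she should continue to be followed in the study per the" Schedule of Activities. Pregnancy is the exception: under Protocol 10.5.3 "the subject must not receive or apply further investigational product and must be discontinued from the study". Protocol 4.1 says that subjects who stop drug early complete Visit 7, which SAP 12.5 labels Week 24. SAP 13.1 counts subjects who are off drug but still in the study, as part of disposition only.

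**The concern.** A reader of the study report will want two facts about local tolerability over 24 weeks: how many children had burning, stinging, itching, scaling or erythema at any time, and how severe it became in each child. A series of by-visit percentages answers neither, because it does not show whether the same subjects or different ones are affected from visit to visit. The endpoint as worded asks for incidence. The described table gives point prevalence at each visit, with a 24-hour recall for the subject-reported symptoms (Protocol 6.6).

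The by-visit percentages could also mix subjects using the gel with subjects who have stopped it, because neither SAP 12.3.1 nor 13.3.1 sets an on-treatment condition. If those who stopped because of a reaction later score zero, the percentages at later visits would look better than the experience of those still applying the gel.

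**Working it through.** There is no planned figure to reproduce. The sample size of up to 24 comes from enrolment in the preceding study (Protocol 11.1, SAP 11), and the documents give no reaction or discontinuation rate. The counts below are therefore assumptions.

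**Inputs from the documents**
- N = 24 at most.
- Tolerability visits after Week 0: Weeks 4, 8, 12, 16, 20 and 24, which is six.
- Week 0 is carried over from Day 8 of the preceding study (Schedule of Activities, footnote b). It follows about 7 days of dosing. Since baseline is the last value before the first dose of that study (SAP 12.4), Week 0 is a post-baseline, on-drug record and makes a seventh assessment.

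**What by-visit counts imply about subjects ever affected**

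Let m_v be the number affected at visit v, with all 24 seen each time. The number ever affected, E, satisfies

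max(m_v) ≤ E ≤ min(24, Σ m_v).

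The lower limit has the same subjects affected throughout; the upper limit has different subjects at every visit.

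| Affected per visit | Visits | Smallest E | Largest E |
|---|---|---|---|
| 1 (4.2%) | 6 | 1 (4.2%) | 6 (25.0%) |
| 2 (8.3%) | 6 | 2 (8.3%) | 12 (50.0%) |
| 2 (8.3%) | 7, with Week 0 | 2 (8.3%) | 14 (58.3%) |
| 4 (16.7%) | 6 | 4 (16.7%) | 24 (100%) |

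The upper limits are logical extremes. As an intermediate case, if each subject had a 2/24 chance at each of six visits independently, the expected proportion ever affected would be 1 − (22/24)^6 = 1 − 0.593 = 40.7%, or about 9.8 of 24.

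The same limits apply to any single grade. One severe score at each of six visits could be one child or six.

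**What off-drug scores could do at one visit**

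If k of 24 subjects are off drug and all score absent, the pooled percentage equals the on-drug percentage × (24 − k)/24. The factor is 0.96 for k = 1, 0.875 for k = 3 and 0.75 for k = 6.

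Take four on-drug subjects with burning and k = 3:
- On drug: 4/21 = 19.0% (exact 95% CI 5.4 to 41.9).
- Pooled: 4/24 = 16.7% (4.7 to 37.4).
- Pooled, if one of the three still has the reaction: 5/24 = 20.8% (7.1 to 42.2).

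The shift is small against the width of the intervals, and its direction is not fixed. The gap between by-visit and ever-affected counts is larger and needs no discontinuations at all.

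**The case against.** The best defence has three parts. First, Protocol 6.6 makes any local reaction that needs concomitant therapy, interrupts treatment or leads to discontinuation an AE as well, and AEs are tabulated once per subject at worst severity. Second, with at most 24 subjects the listings let a reader find each worst score and each stop date by hand. Third, Appendix A is only preliminary, and the text of SAP 13.3.1 does name stinging.

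All of this stands, and it limits the point. It does not remove it. Milder reactions need not become AEs, and the AE scale has three grades (Protocol 10.2.3) against 0 to 4 for tolerability. A primary endpoint should have its own planned table and not depend on reconstruction from listings.

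A reader might infer four stronger things that the documents do not support.

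- *That off-drug records are pooled by rule and dilute the results.* No sentence directs this. It is only the default that follows from continued follow-up with no on-treatment condition. If a subject completes Visit 7 on stopping and then leaves, there may be few or no such records. SAP 13.3.1 also confines these tables to applicable visits, without defining the term.
- *That a later Week 24 score overwrites an early Visit 7.* This requires Visit 7 to be done twice, which follows only from combining Protocol 4.1 with 4.5.1.1. In 4.5.1.1 itself the Early Termination visit is for a subject who refuses to stay. It also stretches the repeat-assessment rule to cover records that may be months apart.
- *That scores from unscheduled visits are lost.* Neither Protocol 7.5 nor the Schedule of Activities requires tolerability scoring at those visits. Any score that is taken would be listed but not summarised.
- *That the patient-reported scores have the same fault to the same degree.* SAP 13.4 likewise sets no on-treatment condition, but those endpoints are exploratory and the matter is slight.

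**Conclusion.** The point holds, and it is minor. The described tolerability tables do not deliver the subject-level incidence or worst severity that the primary endpoint names, although the same section of the SAP already uses the right device for TEAEs. With an assumed 2 of 24 affected at each visit, the tables would fit anything from 2 to 12 subjects ever affected over Weeks 4 to 24, or up to 14 with Week 0. This assumes all 24 are assessed each time. The possible mixing of off-drug scores is secondary, of unknown size and direction, and may be nil.

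One limit remains under any analysis. Subject-reported symptoms are asked about over the previous 24 hours, so reactions that come and go between visits are not scored. A worst-severity table would show the worst that was recorded at assessments, not the worst that occurred.

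**What to change.** In SAP 13.3.1, add for each of burning, stinging, itching, scaling and erythema a table that counts each subject once, at the worst severity (either axilla) at any assessment after the first dose. Include the carried-over Week 0 record, any early Visit 7, and any tolerability score that happens to be taken at an unscheduled visit, stated as an exception to SAP 12.3.1. A maximum is not lowered by later absent scores, and it keeps a reaction first scored after the gel was stopped.

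Keep the by-visit tables on all observed data, so that reactions persisting after stopping are not hidden. Flag records whose 24-hour recall period contains no application, and show the number off drug at each visit. Dosing dates and times are already collected in the diary (Protocol 8.5) and entered in the eCRF (SAP 13.2).

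In Appendix A and Listing 16.2.7.7, replace dryness with stinging.

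The cost is SAP wording, one derived flag and a few extra displays. Sample size, visits and the burden on subjects do not change.

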#### 13.3.2 Pharmacokinetics

- Plasma concentrations of sofpironium and BBI-4010, will be determined using validated liquid chromatography with tandem mass spectrometry (LC-MS/MS) analytical methods. The lower limit of quantification (LLQ) of the assay in plasma is

0.0555 ng/mL for both sofrironium and BBI-4010. Specifics of the analytical procedures will be provided in separate bioanalytical documentation.

- Individual plasma  $C_{trough}$  values of sofrironium and BBI-4010 will be summarized descriptively using the arithmetic mean, SD, CV (%), median, minimum and maximum. Mean ( $\pm$ SD)  $C_{trough}$  values will also be presented graphically by week to assess exposure, accumulation and steady state

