### 7.3.2 Pharmacokinetics

- Plasma samples will be collected  $\geq$ 12 hours after the last dose on Week 0 (Day 1) [per Day 8/Visit 4 of Study BBI-4000-CL-105], Week 4 (Day 28 [ $\pm$ 3 days]), and Week 24 (Day 168 [ $\pm$ 5 days]).

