## 11 SAMPLE SIZE

Sample size is based on the planned enrollment under Study BBI-4000-CL-105. Up to 24 subjects may participate in this study.

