## 12 GENERAL CONSIDERATIONS FOR DATA ANALYSIS

### 12.1 Analysis Populations

Two populations will be used for analysis: Safety and PK. The definition of these populations follows:

- **Safety Population:** All enrolled subjects who applied at least one dose of study drug and have at least one post-baseline safety assessment.
- **Pharmacokinetic Population:** All enrolled subjects who applied at least one dose of study drug and have at least one quantifiable PK sample for analysis.

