### **12.3.2 Pharmacokinetics**

- The PK population will be used for evaluation of PK parameters.
- All plasma PK parameter calculations ( $C_{trough}$  values) will be performed using actual time points (actual date and time of each blood draw) calculated relative to the time of study drug administration.
- Graphical comparison of  $C_{trough}$  values (collected  $\geq 12$  hours after the prior dose) on Week 0 (Day 1), Week 4 (Day 28  $\pm 3$  days), and Week 24 (Day 168 [ $\pm 5$  days]) will be used to assess steady state levels.
- All descriptive analyses and generation of tables, listings and figures, will be performed using a validated installation of Phoenix WinNonlin® version 8.0 (Pharsight, Cary, North Carolina, USA) as part of a 21 CFR Part 11 compliant database system (Pharsight Knowledgebase Server “PKS”).
- The final analysis will be conducted after all subjects have completed the study, all PK samples collected, have been analyzed, and the database is locked.
- Subject demographics, baseline characteristics, disposition, dosing dates and dosing times, and compliance data necessary to support analysis of PK, will be imported (SAS datasets) from the clinical safety and efficacy database (eCRF data).
- If additional analyses are required to supplement the planned PK analyses, they may be performed and will be identified in the appropriate section of the CSR. Any substantial deviations from the planned SAP will be updated in the SAP and approved.

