### **12.3.3 Handling of PK Concentration Values Below the Limit of Quantification**

The lower limit of quantification of the assay in plasma is 0.0555 ng/mL for both sofpironium and BBI-4010. Concentrations that are reported as below the limit of quantitation will be set to 0 for the calculation of the descriptive statistics for the drug concentration summary.

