## Figures

### Table of Content for Figures

Figure 14.x.x.1 Mean ( $\pm$ SD) Sofpironium Plasma Concentrations (Ctrough) versus Week (Linear Scale)

Figure 14.x.x.2 Mean ( $\pm$ SD) Primary Metabolite Plasma Concentrations (Ctrough) versus Week (Linear Scale)

Figure 14.x.x.3 Overlaid Individual Sofpironium Plasma Concentrations (Ctrough) versus Week (Linear Scale)

Figure 14.x.x.4 Overlaid Individual Primary Metabolite Plasma Concentrations (Ctrough) versus Week (Linear Scale)

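### Accumulation and steady state are assessed by eye only; repeated troughs from the same subjects get no within-subject ratio or interval

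*SAP*

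**What the plan says.** Systemic exposure, measured as trough concentration, is a primary objective (SAP 7.1.1.2), and the Week 4 and Week 24 troughs are a primary endpoint (SAP 7.2.1.2). SAP 7.3.2 takes a trough at Week 0, which is the Day 8 sample of CL-105, and again at Week 4 and Week 24.

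The analysis has three parts:

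- **Numerical:** troughs are "summarized descriptively using the arithmetic mean, SD, CV (%), median, minimum and maximum" (SAP 13.3.2). The PK tables in Appendix B give these statistics by week and nothing else.
- **Graphical, means:** mean (±SD) "values will also be presented graphically by week to assess exposure, accumulation and steady state" (SAP 13.3.2; Protocol 11.4.2 plans the same graph). SAP 12.3.2 says that a graphical comparison of the Week 0, Week 4 and Week 24 troughs "will be used to assess steady state levels".
- **Graphical, individuals:** Appendix B lists "Overlaid Individual Sofpironium Plasma Concentrations" by week, a matching figure for the metabolite, and individual listings with sampling times.

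Three further rules matter. PK-population subjects must "have at least one quantifiable PK sample for analysis", so one sample suffices (SAP 12.1). "Concentrations that are reported as below the limit of quantitation will be set to 0 for the calculation of the descriptive statistics" (SAP 12.3.3), with a quantification limit of 0.0555 ng/mL. On numbers, "Up to 24 subjects may participate in this study" (SAP 11).

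**The concern.** The SAP sets out to assess accumulation and steady state, which are questions about change within a subject, but plans no estimate of that change. A reader of the report will have week means, SD bars and a set of overlaid lines, with no figure for how large a rise the data can exclude.

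The mean plot is poorly suited to this. An SD bar describes spread between subjects and does not shrink as subjects are added. If the between-subject CV were 100% (assumed), the SD would equal the mean, so a true doubling would only reach the tip of the earlier week's upper bar.

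The week means may also come from different subjects. One quantifiable sample is enough for the PK population, missing values stay missing (SAP 12.3.4), and values may be excluded case by case (SAP 12.3.5). The early-termination visit shares the Week 24 label (SAP 12.5), so an early terminator's sample could enter the Week 24 mean.

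The SAP does plan changes from baseline for laboratory values (13.3.1) and for the exploratory HDSM-Ax and PGI-S (13.4). The primary PK data have no counterpart.

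**Working it through.** **Plan's own figure.** There is none to reproduce. The 24 is an enrollment cap carried over from CL-105, and no precision or variability is stated for PK.

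**Inputs.** n = 24 pairs is the ceiling from SAP 11. The CV of the troughs, the within-subject correlation ρ and the BLQ rate are assumptions shown over a range, because the documents give none of them. Troughs are taken as log-normal.

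**Formulas.** The log-scale SD is s = √ln(1 + CV²). For a ratio of two weeks, the 90% half-widths on the log scale are:

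- unpaired: t(0.95; 2n − 2) × s × √(2/n)
- paired: t(0.95; n − 1) × s × √(2(1 − ρ)/n)

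The unpaired interval is a yardstick for what comparing two week means could offer. The plan itself gives no interval.

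**One case in full (CV 100%, n = 24).** s = √ln 2 = 0.833.

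- Unpaired: 1.679 × 0.833 × √(2/24) = 0.404, a factor of exp(0.404) = 1.50 either way.
- Paired, ρ = 0.5: 1.714 × 0.833 × √(1/24) = 0.291, a factor of 1.34.
- Relative width: 0.291/0.404 = 0.72, a narrowing of 28%.

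**Range at n = 24, CV 100%.**

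| ρ | Paired factor (unpaired 1.50) | Log width, paired/unpaired |
|---|---|---|
| 0 | 1.51 | 1.02 |
| 0.3 | 1.41 | 0.85 |
| 0.5 | 1.34 | 0.72 |
| 0.7 | 1.25 | 0.56 |
| 0.8 | 1.20 | 0.46 |
| 0.9 | 1.14 | 0.32 |

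The last column does not depend on the CV, because s cancels. The factors do. At CV 50% they are 1.26 unpaired, 1.18 at ρ = 0.5 and 1.11 at ρ = 0.8. At CV 150% they are 1.69, 1.46 and 1.27.

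**Fewer pairs (CV 100%).** With 18 pairs the factors are 1.60 unpaired, 1.41 at ρ = 0.5 and 1.24 at ρ = 0.8. With 12 pairs they are 1.79, 1.54 and 1.31.

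**BLQ values.** If a fraction q of samples is BLQ, the pairs quantifiable at both visits number 24(1 − q)² when BLQ status is independent across visits and 24(1 − q) when it is fully concordant.

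| q | Pairs left of 24 |
|---|---|
| 10% | 19.4 to 21.6 |
| 25% | 13.5 to 18 |
| 50% | 6 to 12 |
| 75% | 1.5 to 6 |

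In a simulation at CV 100% and 50% BLQ, using only pairs quantifiable at both visits, about 8 pairs remained at ρ = 0.5 (median factor 1.50) and about 9.5 at ρ = 0.8 (1.30).

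**Effect of the BLQ rule on a ratio.** With BLQ set to 0, a log ratio is undefined. Dropping such pairs removes subjects who rise from BLQ to quantifiable, the pattern that accumulation would produce, so the estimate can be pulled toward no change. With LLQ/2 = 0.0555/2 = 0.02775 ng/mL, a rise from BLQ gives a ratio of at least 0.0555/0.02775 = 2, and a pair that is BLQ at both visits gives exactly 1. Neither rule is neutral, so the pair counts are needed beside the ratios.

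**The case against.** The best defense is that the pairing is not ignored. The overlaid individual figures and the listings show each subject's course for both analytes, and the comparison in SAP 12.3.2 is of trough values, not only of means. A reader who infers that the plan looks at mean plots alone, or that it hides within-subject change altogether, goes beyond the documents. What stands is that these displays are still read by eye and yield no estimate.

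A second tempting inference is that pairing would bring far better precision. It can be made to look so. With a between-subject CV of 100%, a within-subject CV of 50% and 24 pairs, the factors are 1.26 paired and 1.59 unpaired. With CVs of 60% and 40%, they are 1.21 and 1.39. Those choices imply correlations of about 0.76 (0.693/0.916) and 0.67 (0.307/0.456), and they assume no dropout and no BLQ values. No figure in the documents supports them.

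Third, ratios would not settle accumulation. CL-105 lasts about 7 days (SAP 2.2), so the Week 0 trough already follows a week of dosing. The sampling window, from 12 hours after a dose until the next dose (SAP 12.3.6), also adds timing noise to any ratio. Both points stand and limit what the table may be said to show.

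Finally, the endpoint is determination of the troughs, which the by-week tables deliver. Accumulation and steady state are named as purposes of a graph, no hypothesis is tested, and SAP 12.3.2 allows supplementary PK analyses. This bears on how serious the gap is. It does not argue against prespecifying an estimate from data already collected.

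**Conclusion.** The point holds as a gap in a descriptive analysis. Assessment of accumulation and steady state is graphical only, through means and individual overlays, and troughs repeated by design on a primary objective get no within-subject estimate or interval.

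The benefit of adding one has two parts. The first does not depend on the correlation: the report would state a change with its uncertainty. The second is precision, and it is conditional. With 24 complete pairs and log-normal troughs, the interval narrows by about 15% at ρ = 0.3, 28% at 0.5 and 54% at 0.8, and not at all at ρ = 0. Dropout or frequent BLQ values could use up much of that. At 50% BLQ and ρ = 0.5, the paired factor of 1.50 merely equals the unpaired one for 24 subjects per week with no BLQ.

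The planned PK summaries remain valid and reportable. The change is worth making because it is cheap and answers a question that the SAP itself raises.

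**What to change.** Add to SAP 13.3.2 and Appendix B one table per analyte of within-subject ratios: Week 4/Week 0, Week 24/Week 4 and Week 24/Week 0. Analyze on the log scale and report the geometric mean ratio, 90% interval and number of pairs. Restrict it to samples with a documented prior dose and a documented sampling time inside the trough window. For this table, that replaces the SAP 12.3.4 fallback to the scheduled time.

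State a BLQ rule for this table separate from SAP 12.3.3:

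- Report the number of pairs moving from BLQ to quantifiable, from quantifiable to BLQ, and BLQ at both visits.
- Give the ratio for pairs quantifiable at both visits, and again with BLQ replaced by LLQ/2 or from a censored-data model, so that rises from BLQ are not lost.

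Label the ratios to Week 0 as change after about 7 days of dosing, not accumulation from first dose. Keep the planned mean and individual figures.

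SAP 12.3.7 already sets rounding for the geometric mean and geometric CV, although 13.3.2 and the PK tables list neither, so log-scale output fits the existing conventions. The cost is the extra table and a BLQ rule that rests on an assumption. No new data are needed.
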